## Appendix 8. Reasonably Anticipated Serious Adverse Events

---

### Reasonably Anticipated Serious Adverse Events

---

#### Indication or Study Population: Type 2 Diabetes Mellitus

**Group 1:** Anticipated comorbidities expected to be reported as serious adverse events in clinical studies:

- Myocardial infarction (fatal and nonfatal)a
- Cerebral vascular accident (fatal and nonfatal)b
- Myocardial ischemiac
- Peripheral vascular diseased
- Infections

**Group 2:** Events which may or may not be anticipated comorbidities of type 2 diabetes mellitus, may infrequently be reported as serious adverse events in clinical studies:

- Retinopathye
- Nephropathyf
- Neuropathyg
- Sudden death and cardiovascular death not due to myocardial infarction or stroke
- Cardiac failure
- Diabetic ketoacidosis
- Diabetic foot
- Fractures
- Neoplasia
- Hypoglycemia
- Hyperglycemic hyperosmolar syndrome or state

---

**Examples of terms in the categories above include, but are not limited to:**

- a Acute myocardial infarction, myocardial infarction, acute coronary syndrome.
- b Cerebrovascular accident, stroke, cerebral infarct, ischemic cerebral infarction, ischemic stroke, transient ischemic attack.
- c Angina, unstable angina, acute coronary syndrome, coronary artery disease, coronary artery bypass graft, percutaneous coronary intervention, coronary angioplasty.
- d Peripheral vascular disease, diabetic peripheral vascular disease, diabetic vascular disease, carotid endarterectomy, peripheral revascularization.
- e Blindness, proliferative retinopathy, nonproliferative (background) retinopathy, diabetic retinopathy, retinal laser coagulation, photocoagulation, loss of vision.
- f Diabetic nephropathy, renal failure, acute renal failure, renal insufficiency. Should not include terms associated with prerenal azotemia due to dehydration.
- g Peripheral neuropathy, mononeuropathy, autonomic neuropathy, orthostatic or postural hypotension.

---

## Appendix 9. Permitted Medications for Subjects with Hepatic Impairment

---

Examples of permitted medications in subjects with hepatic impairment are presented in the table below, which serves as a guidance and is neither intended to be prescriptive nor exhaustive. Other drugs not listed in this table (such as antihypertensive agents) may be authorized during the study at the discretion of the sponsor and investigator.

Therapeutic Category	Drugs
Antibiotics	Ofloxacin Norfloxacin Neomycin
Pruritus Treatment	Ursodeoxycholic acid Cholestyramine
Nutritional supplementation	Vitamins A, D, E, K and Calcium
Diuretics	Furosemide Spironolactone Hydrochlorothiazide
Ammonium Detoxicant	Lactulose Neomycin Metronidazole Rifaximin
Immunosuppressive agents	Corticosteroids Interferon $\alpha$ 2a Interferon $\alpha$ 2b
Antivirals	Lamivudine Ribavirin Entecavir Ledipasvir/Sofosbuvir

---

---

**Appendix 10. Protocol Amendment I8F-MC-GPGQ(a)  
Summary - A Single Dose Pharmacokinetic Study of  
Tirzepatide in Subjects with Varying Degrees of Hepatic  
Impairment**

---

## Overview

Protocol I8F-MC-GPGQ, A Single Dose Pharmacokinetic Study of Tirzepatide in Subjects with Varying Degrees of Hepatic Impairment, has been amended. The new protocol is indicated by Amendment (a) and will be used to conduct the study in place of any preceding version of the protocol.

The overall changes and rationale for the changes made to this protocol are as follows:

- Provide improved clarity on when additional hepatic monitoring tests, as described in Appendix 4, should be performed. There is a need to differentiate between the cut-off trigger for testing in subjects with normal liver function enzyme tests and patients with hepatic impairment with elevated baseline liver enzymes.
  - Amended Section 9.4.7.1.
  - Added Section 9.4.7.2.
- Added clarification to Exclusion Criterion [37] to apply only to Group 1 healthy controls.
- Added clarification to Exclusion Criterion [60] specifying systemic glucocorticoids.
- Minor editorial changes and formatting corrections were made but not necessarily detailed below.

## Revised Protocol Sections

**Note:** All deletions have been identified by ~~strikethroughs~~.  
All additions have been identified by the use of underscore.

### **6.2.1. Exclusion Criteria for All Subjects Unless Otherwise Specified**

[37] show evidence of hepatitis B and/or positive hepatitis B surface antigen (applies to Group 1 control subjects only)

### **6.2.3. Additional Exclusion Criteria for Subjects with T2DM and Hepatic Impairment**

[60] have received chronic (lasting >14 consecutive days) systemic glucocorticoid therapy (excluding topical, intra-articular, and inhaled preparations) in the past year or have received any systemic glucocorticoid therapy within 30 days before screening

### **9.4.7.1. Hepatic Safety Monitoring in Subjects with Treatment-emergent Abnormal Liver Tests**

~~If a study subject experiences elevated ALT  $\geq 3 \times$  ULN, ALP  $\geq 2 \times$  ULN, or elevated total bilirubin  $\geq 2 \times$  ULN, liver tests (Appendix 4) should be repeated within 3 to 5 days including ALT, AST, ALP, total bilirubin, gamma-glutamyl transferase, and creatinine phosphokinase to confirm the abnormality and to determine if it is increasing or decreasing. If the abnormality persists or worsens, clinical and laboratory monitoring should be initiated by the investigator based on consultation with the Lilly CP or CRP. Monitoring should continue until levels normalize and/or are returning to approximate baseline levels.~~

~~Additional safety data should be collected if 1 or more of the following conditions occur:~~

- ~~elevation of serum ALT to  $\geq 5 \times$  ULN on 2 or more consecutive blood tests~~
- ~~elevated total bilirubin to  $\geq 2 \times$  ULN (except for cases of known Gilbert's syndrome)~~
- ~~elevation of serum ALP to  $\geq 2 \times$  ULN on 2 or more consecutive blood tests~~
- ~~hepatic event considered to be an SAE~~

### **Abnormal liver tests in study participants with normal or near normal baseline ALT, AST, ALP, and total bilirubin (TBL; $<1.5 \times$ ULN)**

~~If a subject who was enrolled with baseline ALT, AST, ALP, TBL  $<1.5 \times$  ULN, experiences elevated ALT  $>3 \times$  ULN, ALP  $>2 \times$  ULN, or TBL  $>2 \times$  ULN, liver tests (Appendix 4) should be repeated within 48 to 72 hours, including ALT, AST, ALP, TBL, gamma-glutamyl transferase (GGT), and creatine kinase (CK) to confirm the abnormality and to determine if it is increasing or decreasing.~~

~~If the abnormality persists or worsens, clinical and laboratory monitoring, and evaluation for possible causes of abnormal liver tests should be initiated by the investigator in consultation with~~

the Lilly CP or CRP. Monitoring should continue until levels normalize and/or are returning to approximate baseline levels.

**Elevated ALT/AST in subjects with baseline ALT/AST >1.5× ULN**

If a subject, who was enrolled with baseline ALT/AST >1.5× ULN, experiences elevated ALT/AST >2× baseline (respectively), liver tests (Appendix 4) should be repeated within 48 to 72 hours, including ALT, AST, ALP, TBL, GGT, and CK to confirm the abnormality and to determine if it is increasing or decreasing.

If the abnormality persists or worsens, clinical and laboratory monitoring, and evaluation for possible causes of abnormal liver tests should be initiated by the investigator in consultation with the Lilly CP or CRP. Monitoring should continue until levels normalize and/or are returning to approximate baseline levels.

**Elevated ALP in subjects with baseline ALP >1.5× ULN**

If a subject, who was enrolled with baseline ALP >1.5× ULN, experiences elevated ALP >2× baseline, liver tests (Appendix 4) should be repeated within 48 to 72 hours, including ALT, AST, ALP, TBL, GGT, and CK to confirm the abnormality and to determine if it is increasing or decreasing.

If the abnormality persists or worsens, clinical and laboratory monitoring, and evaluation for possible causes of abnormal liver tests should be initiated by the investigator in consultation with the Lilly CP or CRP. Monitoring should continue until levels normalize and/or are returning to approximate baseline levels.

**Elevated TBL in subjects with baseline TBL >1.5× ULN**

If a subject, who was enrolled with baseline TBL >1.5× ULN, experiences elevated TBL >1.5× baseline, liver tests (Appendix 4) should be repeated within 48 to 72 hours, including ALT, AST, ALP, TBL, direct bilirubin, GGT, and CK to confirm the abnormality and to determine if it is increasing or decreasing.

If the abnormality persists or worsens, clinical and laboratory monitoring, and evaluation for possible causes of abnormal liver tests should be initiated by the investigator in consultation with the Lilly CP or CRP. Monitoring should continue until levels normalize and/or are returning to approximate baseline levels.

**9.4.7.2 Additional Hepatic Data Collection (Hepatic Safety eCRF) in Subjects with Treatment-emergent Abnormal Liver Tests**

**Treatment-emergent abnormal liver tests in subjects with normal or near normal baseline ALT, AST, ALP, and TBL (<1.5× ULN)**

In a subject, who was enrolled with baseline ALT, AST, ALP, and TBL < 1.5× ULN, additional hepatic safety data should be collected, if 1 or more of the following conditions occur:

- elevation of serum ALT to > 5× ULN on 2 or more consecutive blood tests

- elevated total bilirubin to  $>2\times$  ULN (except for cases of known Gilbert's syndrome)
- elevation of serum ALP to  $\geq 2\times$  ULN on 2 or more consecutive blood tests
- hepatic event considered to be a SAE

*Elevated ALT/AST in subjects with baseline ALT/AST  $\geq 1.5\times$  ULN*

In a subject, who was enrolled with baseline ALT/AST  $>1.5\times$  ULN, elevated ALT/AST  $>3\times$  baseline (respectively) on two or more consecutive tests should prompt additional hepatic safety data collection.

*Abnormal ALP in subjects with baseline ALP  $>1.5\times$  ULN*

In a subject, who was enrolled with baseline ALP  $>1.5\times$  ULN, elevated ALP  $>2\times$  baseline on two or more consecutive tests should prompt additional hepatic safety data collection.

*Abnormal TBL in subjects with baseline TBL  $\geq 1.5\times$  ULN*

In a subject, who was enrolled with baseline TBL  $>1.5\times$  ULN, elevated TBL  $>2\times$  baseline on two or more consecutive tests should prompt additional hepatic safety data collection.

Leo Document ID = 5ae2361e-edc8-47c2-9448-f4b8f0a367f8

Approver: PPD

Approval Date & Time: 17-Jul-2019 14:59:24 GMT

Signature meaning: Approved

Approver: PPD

Approval Date & Time: 18-Jul-2019 19:26:21 GMT

Signature meaning: Approved

2. ABBREVIATIONS

Abbreviations pertain to the Statistical Analysis Plan (SAP) only (not the tables, figures and listings [TFLs]).

%AUC($t_{last}-\infty$)	Percentage of AUC(0- ∞) extrapolated
ADA	Anti-drug antibody
AE	Adverse event
ANCOVA	Analysis of covariance
AUC	Area under the concentration versus time curve
AUC(0- t_{last})	Area under the concentration versus time curve from time zero to time t , where t is the last time point with a measurable concentration
AUC(0- ∞)	Area under the concentration versus time curve from time zero to infinity
BQL	Below the lower limit of quantitation
CI	Confidence interval
CL/F	Apparent total body clearance of drug calculated after extra vascular administration
C_{last}	Last quantifiable drug concentration
C_{max}	Maximum observed drug concentration
CP	Child-Pugh
CRU	Clinical Research Unit
CSR	Clinical Study Report
CV	Coefficient of variation
EC	Early Clinical
ECG	Electrocardiogram
ICH	International Conference on Harmonisation
INR	International normalized ratio
LLOQ	Lower limit of quantitation
PD	Pharmacodynamic
PK	Pharmacokinetic
SAP	Statistical Analysis Plan
SC	Subcutaneous
SD	Standard deviation
$t_{1/2}$	Half-life associated with the terminal rate constant (λ_z) in

	non-compartmental analysis
T2DM	Type 2 diabetes mellitus
TFLs	Tables, Figures, and Listings
t_{\max}	Time of maximum observed drug concentration
ULN	Upper limit of normal
V_{ss}/F	Apparent volume of distribution at steady state after extra-vascular administration
V_z/F	Apparent volume of distribution during the terminal phase after extra-vascular administration

3. INTRODUCTION

This SAP has been developed after review of the Clinical Study Protocol (final version dated 01 April 2019).

This SAP describes the planned analysis of the safety, tolerability, pharmacokinetic (PK) and pharmacodynamic (PD) data from this study. A detailed description of the planned TFLs to be presented in the clinical study report (CSR) is provided in the accompanying TFL shell document.

The intent of this document is to provide guidance for the statistical and PK analyses of data. In general, the analyses are based on information from the protocol, unless they have been modified by agreement between Eli Lilly and Company and Covance Early Clinical (EC) Biometrics. A limited amount of information concerning this study (e.g., objectives, study design) is given to help the reader's interpretation. This SAP must be signed off prior to first subject administration for this study. When the SAP and TFL shells are agreed upon and finalized, they will serve as the template for this study's CSR.

This SAP supersedes the statistical considerations identified in the protocol; where considerations are substantially different, they will be so identified. If additional analyses are required to supplement the planned analyses described in this SAP, they may be performed and will be identified in the CSR. Any substantial deviations from this SAP will be agreed upon between Eli Lilly and Company and Covance EC Biometrics and identified in the CSR. Any minor deviations from the TFLs may not be documented in the CSR.

This SAP is written with consideration of the recommendations outlined in the International Conference on Harmonisation (ICH) E9 Guideline entitled Guidance for Industry: Statistical Principles for Clinical Trials¹ and the ICH E3 Guideline entitled Guidance for Industry: Structure and Content of Clinical Study Reports².

4. STUDY OBJECTIVES

4.1 Primary Objective

- To evaluate the PK of a single subcutaneous (SC) dose of tirzepatide in subjects with mild, moderate, and severe hepatic impairment compared to control subjects with normal hepatic function.

4.2 Secondary Objective

- To evaluate the safety and tolerability of a single SC dose of tirzepatide in subjects with mild, moderate, and severe hepatic impairment compared to control subjects with normal hepatic function.

4.3 Exploratory Objective

- To evaluate the formation of anti-drug antibodies (ADA) to tirzepatide after a single 5-mg SC dose administered to subjects with mild, moderate, or severe hepatic impairment compared to control subjects with normal hepatic function.

5. STUDY DESIGN

This will be a multicenter, parallel, single-dose, open-label, single-period study of tirzepatide in subjects with normal hepatic function and subjects with mild, moderate, and severe hepatic impairment. Subjects who have a concomitant type 2 diabetes mellitus (T2DM) diagnosis will not be specifically excluded.

Subjects will be enrolled within the following groups:

- Group 1: at least 6 subjects and up to 12 subjects with normal hepatic function (Control).
- Group 2: at least 6 subjects with mild hepatic impairment (Child-Pugh [CP] A).
- Group 3: at least 6 subjects with moderate hepatic impairment (CP B).
- Group 4: up to 6 subjects with severe hepatic impairment (CP C).

Efforts will be made to achieve 6 completers with severe hepatic impairment (Group 4); however, acknowledging the difficulty in recruiting this subject population, 2 to 3 subjects with severe hepatic impairment may be an acceptable target.

[figure not shown]
The Child-Pugh classification is described in Section [5.1](#).

Subjects enrolled in Group 1 (normal hepatic function) will be matched by weight (± 10 kg), age (± 10 years), and sex to subjects in Groups 2 through 4, as far as practically possible. Subjects with normal hepatic function cannot be matched to more than 1 hepatically-impaired subject within an impairment group; however, subjects with normal hepatic function may be matched to 1 subject from more than 1 hepatic impairment group, therefore requiring fewer subjects to be enrolled to Group 1 (minimum of 6). Subjects who withdraw before completing all study procedures may be replaced at the discretion of the investigator in discussion with the sponsor.

Subjects will undergo a screening examination within 28 days prior to enrollment, check in to the clinical research unit (CRU) on Day -1, and receive a single SC dose of 5 mg tirzepatide on Day 1, following an overnight fast of at least 8 hours. Subjects will remain at the CRU until discharge on Day 5, and return to the CRU on Days 8 and 15 for PK blood sampling and other study procedures. Each subject will be required to return to the CRU for a follow-up visit and final PK blood sample collection at least 28 days postdose.

PK blood sampling and safety assessments, including vital sign measurement, physical examination, clinical laboratory tests, electrocardiograms (ECGs), and adverse event (AE) recording, will be performed.

Subjects with normal hepatic function and with mild and moderate hepatic impairment (Groups 1 to 3) can be dosed concurrently ([Figure GPGQ.1](#)). Dosing of the first subject in Group 4 (severe hepatic impairment) may proceed only after satisfactory review of safety, tolerability, and PK data from at least 2 subjects in Group 2 (mild hepatic impairment), at least 2 subjects in Group 3 (moderate hepatic impairment), and at least 2 subjects in Group 1 (appropriate matched-control subjects with normal hepatic function). Based on continuous review of safety and tolerability data, the dose of tirzepatide may be reduced to 2.5 mg for the remainder of subjects in Groups 2 and 3 (mild and moderate impairment) and all subjects in Group 4 (severe impairment), as well as for control subjects in Group 1.

Note: dosing of the first subject with severe hepatic impairment (Group 4) may proceed only after satisfactory review of safety, tolerability and PK data from at least 2 subjects with mild hepatic impairment (Group 2), and at least 2 subjects with moderate hepatic impairment (Group 3), and at least 2 subjects in Group 1 (appropriate matched-control subjects with normal hepatic function).

Figure GPGQ.1. Illustration of study design for Protocol I8F-MC-GPGQ

The total duration of study participation for each subject (from screening through follow-up visit) is anticipated to be approximately 8 weeks.

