Study GPGA was a combination single-ascending dose (SAD) and a multiple ascending-dose (MAD) study in healthy subjects (Part A and B) and a multi-dose study in patients with T2DM (Part C). The study investigated the safety, tolerability, PK, and pharmacodynamics (PD) of tirzepatide administered as SC injections. Weekly doses of tirzepatide ranged from 0.25 mg to 8 mg in the SAD. Maximum tolerated dose in healthy subjects following single-dose administration was 5 mg. In the 4-week MAD part of the study, doses up to 10 mg in healthy subjects or 15 mg in patients with T2DM were attained via a dose escalation approach. A dose of 15 mg tirzepatide attained by fast dose escalation over 4 weeks (5/5/10/15 mg), while considered to be safe, was associated with high incidence of gastrointestinal (GI) events. Terminal half-life was estimated to be approximately 5 days, thus supporting a once weekly dosing regimen, with maximum observed drug concentration ( $C_{max}$ ) occurring between 24 to 72 hours postdose, and steady-state tirzepatide exposures expected to be attained within 4 weeks of once weekly dosing. Study GPGC was a MAD study to investigate the safety, tolerability, PK, and PD in Japanese patients with T2DM. Overall, tirzepatide PK parameters in Japanese patients with T2DM appeared comparable to corresponding parameters from non-Japanese patients with T2DM observed in Study GPGA.

Gastrointestinal adverse events (AEs) (nausea, vomiting, diarrhea, abdominal distension) and decreased appetite were the most frequently reported events by both healthy subjects and patients with T2DM and were dose related in the two Phase 1 studies. A dose-dependent increase in heart rate was detected for both healthy subjects and patients with T2DM who received tirzepatide, similar to what was observed with selective GLP-1 receptor agonists. A few subjects experienced transient elevations in lipase and/or amylase levels, but these episodes were not associated with any relevant clinical outcomes. There were no other clinically relevant safety observations in the Phase 1 studies.

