9. STATISTICAL METHODOLOGY

9.1 General

Data listings will be provided for all data that is databased. Summary statistics and statistical analysis will only be presented for data where detailed in this SAP. For continuous data, summary statistics will include the arithmetic mean, arithmetic standard deviation (SD), median, min, max and N; for log-normal data (e.g. the PK parameters: area under the concentration versus time curve [AUC] and maximum observed drug concentration [C_{max}]) the geometric mean and geometric coefficient of variation (CV%) will also be presented. For categorical data, frequency count and percentages will be presented. Data listings will be provided for all subjects up to the point of withdrawal, with any subjects excluded from the relevant population highlighted. Summary statistics and statistical analyses will generally only be performed for subjects included in the relevant analysis population. For the calculation of summary statistics and statistical analysis, unrounded data will be used.

Mean change from baseline is the mean of all individual subjects' change from baseline values. Each individual change from baseline will be calculated by subtracting the individual subject's baseline value from the value at the timepoint. The individual subject's change from baseline values will be used to calculate the mean change from baseline using a SAS procedure such as Proc Univariate.

Data analysis will be performed using SAS[®] Version 9.4 or greater.

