9.5 Safety and Tolerability Assessments

9.5.1 Adverse events

Where changes in severity are recorded in the Case Report Form (CRF), each separate severity of the AE will be reported in the listings, only the most severe will be used in the summary tables. A pre-existing condition is defined as an AE that starts before the subject has provided written informed consent and is ongoing at consent. A non-treatment emergent AE is defined as an AE which starts after informed consent but prior to dosing. A treatment-emergent AE is defined as an AE which occurs postdose or which is present prior to dosing and becomes more severe postdose.

All AEs will be listed. Treatment-emergent AEs will be summarized by group, severity and relationship to the study drug. The frequency (the number of AEs, the number of subjects experiencing an AE and the percentage of subjects experiencing an AE) of treatment-emergent AEs will be summarized by group, Medical Dictionary for Regulatory Activities (MedDRA) version 21.1 system organ class and preferred term. The summary and frequency AE tables will be presented for all causalities and those considered related to the study drug. Any serious AEs will be listed.

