9.5.5 Vital signs

Vital signs data will be summarized by group together with changes from baseline, where baseline is defined as the Day 1 predose assessment. Figures of mean vital signs and mean changes from baseline profiles will be presented by group.

Furthermore, values for individual subjects will be listed.

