10. INTERIM ANALYSES

One interim analysis is planned to occur during Study GPGQ. Two subjects each from Groups 2 and 3 (subjects with mild and moderate hepatic impairment, respectively) and at least 2 subjects in Group 1 (appropriate matched-control subjects with normal hepatic function) will be enrolled in parallel and dosed with 5 mg tirzepatide, followed by an interim analysis to evaluate safety, tolerability, and PK data. Based on this interim analysis, dosing will either continue at 5 mg or be reduced to 2.5 mg for the remaining subjects subjects in Groups 2 and 3 (mild and moderate impairment) and all subjects in Group 4 (severe impairment), as well as for control subjects in Group 1. The final dose determinations will be made by the investigator and the Lilly study team.

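### If the dose is cut to 2.5 mg, the planned safety tables would mix doses within hepatic group under a 5 mg label, biased towards reassurance in the severe group

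*SAP*

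**What the plan says.** The reduction is a foreseen branch of the design. SAP Section 5 states that "the dose of tirzepatide may be reduced to 2.5 mg for the remainder of subjects in Groups 2 and 3". SAP Section 10 applies it to "all subjects in Group 4 (severe impairment), as well as for control subjects in Group 1". Before the planned decision, two subjects each in Groups 2 and 3 and at least two controls "will be enrolled in parallel and dosed with 5 mg tirzepatide, followed by an interim analysis to evaluate safety, tolerability, and PK data". Protocol 5.1, 5.5 and 10.3.5 say the same.

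For PK, SAP 9.3.2 allows dose-normalised parameters after a dose adjustment. No safety section has a counterpart. SAP 9.5.1 states: "Treatment-emergent AEs will be summarized by group, severity and relationship to the study drug". SAP 9.5.5 states: "Vital signs data will be summarized by group together with changes from baseline". SAP 9.5.3 and 9.5.4 group laboratory, hypoglycemia and glucose summaries in the same way. SAP Section 6 lists four hepatic groups and one treatment subheader, 5 mg subcutaneous tirzepatide, for all tables, figures and listings. SAP 9.1 adds: "Summary statistics and statistical analysis will only be presented for data where detailed in this SAP".

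On dose dependence, Protocol 3.2 says that gastrointestinal events and decreased appetite "were dose related in the two Phase 1 studies". It describes the heart-rate increase as dose-dependent and repeats the dose dependence for the mainly gastrointestinal events in Phase 2.

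**The concern.** The secondary objective compares safety and tolerability in each impaired group with controls, and its endpoint is the incidence of adverse events. Incidence cannot be dose-normalised as an AUC can. If the dose is cut, the Group 4 column contains only 2.5 mg subjects while the control column contains a mixture, so a difference between the columns reflects dose as well as hepatic function. For the events the protocol calls dose-related, the dose component lowers the severe column relative to control. The fixed subheader would also label Group 4 with a dose that none of its subjects received.

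Protocol 5.5 and 7.4 link a cut to more safety events or higher exposure than expected in impaired subjects. The tables would therefore become hard to read in the scenario where a hepatic effect is already suspected.

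**Working it through.** **Inputs from the documents.** Controls: 6 to 12. Severe: up to 6, with 2 to 3 acceptable (SAP Sections 5 and 7). Controls at 5 mg before the planned decision: at least 2 (SAP Section 10). This is not a ceiling: SAP Section 5 lets Groups 1 to 3 be dosed concurrently and also ties a reduction to continuous safety review. Severe subjects at 5 mg after a cut: none.

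The only sample-size figure, an enrolment cap of 30, is reproduced by 12 + 6 + 6 + 6 = 30. It has no power basis, and nothing below depends on it.

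**Dose mix after a cut.** Share of controls on 5 mg = k/m. With k = 2 this is 2/12 = 17% to 2/6 = 33%; if all controls were dosed first it is 100%. In Group 4 it is 0%.

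**Assumed event rates.** The documents give none. Take p5 = 50% at 5 mg and p2.5 = 25% at 2.5 mg, with no hepatic effect.

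Expected control incidence = [k × p5 + (m − k) × p2.5] / m. The spurious gap against severe is therefore (k/m) × (p5 − p2.5).

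| Controls on 5 mg | Expected control incidence | Severe | Spurious gap |
|---|---|---|---|
| 2 of 12 | (2 × 0.50 + 10 × 0.25)/12 = 29% | 25% | 4 points |
| 2 of 6 | (2 × 0.50 + 4 × 0.25)/6 = 33% | 25% | 8 points |
| 4 of 6 | (4 × 0.50 + 2 × 0.25)/6 = 42% | 25% | 17 points |
| 6 of 6 | 50% | 25% | 25 points |

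**Sensitivity to the assumed rates.**

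| Rates at 5 mg / 2.5 mg | 2 of 12 controls on 5 mg | 2 of 6 | All |
|---|---|---|---|
| 30% / 20% | 2 points | 3 points | 10 points |
| 40% / 20% | 3 points | 7 points | 20 points |
| 60% / 30% | 5 points | 10 points | 30 points |

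The direction is the same throughout.

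**Masking.** Suppose severe impairment truly raises the 2.5 mg risk from 25% to 40%, an excess of 15 points. Against controls with 2 of 6 on 5 mg, the table would show 40 − 33 = 7 points. With 4 of 6 on 5 mg it would show 40 − 42 = −2, and the excess would disappear.

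**After the fix.** At the same dose the spurious gap is zero by construction. With two controls on 5 mg, 6 − 2 = 4 to 12 − 2 = 10 controls remain as the 2.5 mg comparator. If all controls had been dosed before the cut, none remain.

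**The case against.** The strongest reply is that the plan does not prevent a by-dose table. SAP Section 3 permits supplementary analyses identified in the study report, and Protocol 10.3.1.2 provides for additional safety analysis if warranted. Adverse events are listed by subject, and a dose cut would itself be a prominent result. A reader might infer from SAP 9.1 that a by-dose safety summary is ruled out; the documents do not go that far. What stands is that none is prespecified, while the stated grouping and subheader point the other way. The table shells, which are not among the documents, might add a second subheader, but SAP Section 6 names only one treatment.

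The second reply concerns size. At the planned decision point the expected distortion is 2 × (0.50 − 0.25) = 0.5 of an event in the control group. One subject is 17 points in a group of six, and 33 to 50 points in a severe group of three or two. SAP 9.5.11 plans no inferential safety analysis. This stands: the harm is a misleading descriptive table, not an inflated error rate.

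Three further readings are tempting but unsupported:

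- **Antidrug antibodies.** SAP 9.4.1 names no grouping for the antibody tables, and nothing in the documents says that antibody formation depends on dose.
- **All adverse events.** Dose dependence is stated for gastrointestinal events, decreased appetite and heart rate, not for every event.
- **Mild and moderate groups.** With two of six at 5 mg in each of Groups 1 to 3, the dose mixes are identical. They differ only if accrual or group sizes diverge.

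**Conclusion.** The point holds, conditional on a dose cut. The SAP foresees the cut and adapts PK to it, but leaves the safety layout unchanged. Followed as written, that layout would mislabel the dose for Group 4 and confound dose with hepatic group on the secondary endpoint, towards reassurance in the severe group for the dose-related events.

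Under the assumed rates of 50% and 25% the distortion is about 4 to 8 points with the minimum of two controls at 5 mg. A reader might take the 25-point figure as the expected size. It requires every control to have been dosed before the cut, which concurrent dosing makes possible but which the plan, by extending the reduction to controls, does not intend. All the sizes rest on assumed rates; the direction rests on the protocol's own account of dose dependence. If the dose is never changed, there is no effect.

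**What to change.** Amend SAP Section 6 so that the treatment subheader shows the dose received, and add to SAP 9.5:

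> If the dose is changed during the study, AE, vital-sign, laboratory and glucose summaries will be presented by hepatic group and dose received. Group 4 will be compared descriptively with controls who received the same dose, where any exist; the pooled-dose column is supportive.

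The cost is a few lines of SAP text and some extra table columns, produced only if the dose changes. Dosing and conduct are unaffected. The drawback is small cells: a group of six split at the planned decision point becomes two and four. If all controls were dosed before the change, there is no same-dose comparator; the split table cannot repair that, but it would show it openly.
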